**Registration of Clinical Studies and Disclosure of Results**

The sponsor will register and disclose the existence of and the results of clinical studies as required by law.

**Attachment 1: Modified 6th WM Response Criteria (NCCN 2019) for Investigator Assessment**

Modified WM Response Criteria for Investigator Assessment of Response and Progression	
Category	Response Criteria
Complete Response (CR)	
 
Serum IgM values in normal range
 
Disappearance of monoclonal protein by immunofixation Note: Reconfirmation of CR status is required with a second immunofixation at any time point
 
No histological evidence of bone marrow involvement
 
Complete resolution of lymphadenopathy/splenomegaly if present at baseline
 

Very Good Partial Response (VGPR)	
 
At least 90% reduction of serum IgM from baseline or serum IgM values in normal range
 
Reduction in lymphadenopathy/splenomegaly if present at baseline
 

Partial Response (PR)	
 
At least 50% reduction of serum IgM from baseline
 
Reduction in lymphadenopathy/splenomegaly if present at baseline
 

Minor Response (MR)	
 
At least 25% but <50% reduction of serum IgM from baseline
 

Stable Disease (SD)	
 
Not meeting criteria for CR, VGPR, PR, MR, or progressive disease (PD)
 

Progressive Disease (PD)	
At least one of the following
 
 
A <math>\geq 25\%</math> increase in serum IgM with a total increase of at least 500 mg/dL from nadir 
 
Confirmation of the initial IgM increase is required when IgM is sole criterion for progressive disease.
 
 
 
Appearance of a new lymph nodes <math>>1.5</math> cm in any axis, <math>\geq 50\%</math> increase from nadir in sum of product of diameters (SPD) of more than one node, or <math>\geq 50\%</math> increase in longest diameter of a previously identified node <math>>1</math> cm in short axis
 
Appearance of new splenomegaly or <math>\geq 50\%</math> increase from nadir in enlargement of the spleen
 
Appearance of new extranodal disease2/3
 
New or recurrent involvement in the bone marrow
 
New symptomatic disease on the basis of malignant pleural effusion, Bing Neel (WM CNS disease) syndrome, amyloidosis or light chain deposition disease, or other paraprotein mediated disorder.
 

Abbreviations: CNS= central nervous system; WM= Waldenström's macroglobulinemia

1. Nadir for serum IgM is defined as the lowest serum IgM value obtained at any time from baseline onwards with the exception that serum IgM levels post-plasmapheresis will not be considered for up to 35 days.
2. For additional clarification to assess the appearance or progression of existing nodal and extranodal disease (Refer to Section 9.2.5)
3. Measurable extranodal disease should be assessed in a manner similar to that for nodal disease.
4. Sum of the products of multiple lymph nodes (as evaluated by CT scans) or the longest diameter of one target lymph node.

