### **11.3.2. Secondary Efficacy Endpoints**

#### **11.3.2.1. Clinical Response Rate**

CRR is defined as the proportion of subjects who achieve MR or better according to the modified IVth IWWM (NCCN 2019) criteria as assessed by the investigator. CRR will be analyzed with the exact 2-sided 90% CI based on binomial distribution in a similar fashion as ORR.

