#### 5.3.1. Definition

##### Clinical response rate:

CRR is defined as the proportion of subjects who achieve MR or better according to the modified IVth IWWM (NCCN 2019) criteria as assessed by the investigator.

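### Read literally, Attachment 1 ranks an IgM fall of 50% or more with unreduced baseline nodes or spleen (SD) below a 25% to <50% fall (MR); only the descriptive CRR can be affected

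*Protocol*

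**What the plan says.** The response categories are in Protocol Attachment 1, under the banner "Modified WM Response Criteria for Investigator Assessment of Response and Progression".

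- **MR.** The row opens "At least 25% but" and then caps the IgM reduction below 50%. It has no node or spleen condition.
- **PR.** The IgM condition is "At least 50% reduction of serum IgM from baseline". A second condition, "Reduction in lymphadenopathy" or in splenomegaly, applies if either was present at baseline.
- **VGPR.** IgM must fall by at least 90% or be in the normal range. The node and spleen condition is the same as for PR.
- **CR.** Among other things, baseline lymphadenopathy or splenomegaly must resolve completely.
- **SD.** The residual category: "Not meeting criteria for CR, VGPR, PR, MR, or progressive disease (PD".

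Footnote 4 to the table tells the investigator what to measure, "Sum of the products of multiple lymph nodes (as evaluated by CT scans) or the longest diameter of one target lymph node", but sets no minimum amount of shrinkage.

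The SAP (5.3.1) says "CRR is defined as the proportion of subjects who achieve MR or better". Protocol 11.3.2.1 adds "CRR will be analyzed with the exact 2-sided 90% CI based on binomial distribution in a similar fashion as ORR". Neither document sets a success threshold for CRR.

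**The concern.** Response categories should not get worse as the IgM fall gets deeper, other findings being equal. Here they do. A subject who meets the PR or VGPR level of IgM reduction but whose baseline nodes or spleen have not shrunk fails PR and VGPR on the nodal condition. The same subject fails MR because the fall is too large, and so drops to SD. With a smaller fall and the same nodes, the subject would have been MR.

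CRR is the only endpoint that uses the line between MR and SD. It is the first secondary efficacy endpoint listed, in a study meant to support full approval in China (Protocol 1.2), and with about 17 subjects one classification is visible in the rate. An investigator who meets the case has no written rule for it, and sites could resolve it differently. A rule fixed before the results are seen avoids that question at the analysis.

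**Working it through.** **1. The plan's own figure.** Protocol 11.2 and SAP 1.4 state at least 85% power with about 17 subjects, for ORR 69.8% against 32% at one-sided 0.05. With n = 17, the exact lower 90% limit is 0.311 for 9 responders and 0.364 for 10, so 10 responders are needed to exceed 0.32. The exact error rate is P(X ≥ 10 | 0.32) = 0.0204 and the power is P(X ≥ 10 | 0.698) = 0.892. The stated figure holds. It concerns ORR (PR or better), which does not use the MR/SD line, so nothing below changes it.

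**2. Literal classification.** The Attachment 1 rows are applied as written, assuming no PD criterion is met and IgM is not in the normal range.

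| IgM fall from baseline | Baseline nodes/spleen not reduced | Reduced, or absent at baseline |
|---|---|---|
| 10% | SD | SD |
| 25% | MR | MR |
| 30% | MR | MR |
| 49% | MR | MR |
| 50% | **SD** | PR |
| 60% | **SD** | PR |
| 92% | **SD** | VGPR |

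The middle column reverses at 50%. Changing its three SD cells to MR removes the reversal and leaves every PR and VGPR cell as it was.

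**3. Is it resolved elsewhere?** The footnotes to Attachment 1 cover the IgM nadir, nodal and extranodal progression, and the nodal measure. Protocol 9.2 covers the IgM method, plasmapheresis, and confirmation of PD and CR. Protocol 11.3.2.1 and SAP 5.3.1 and 5.3.2 define and analyse CRR. SAP 5.1.2 covers missing values. None says that a subject who fails PR only on nodes or spleen falls back to MR.

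**4. Endpoints affected.** ORR, DOR and TTR use PR or better. The VGPR rate uses VGPR or better. PFS uses progression or death, and OS uses death. Only CRR uses MR or better.

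**5. Who could be lost.** CRR counts subjects who achieve MR or better, so one qualifying assessment is enough. A subject is lost only if no evaluable assessment lies in the 25% to <50% band and PR or better is never documented. By the Time and Events Schedule, disease is assessed at Weeks 5, 9, 13, 17, 21, 25, 33, 41 and 49, which is 9 visits through Week 49. CT is due at 3 of them (Weeks 17, 33 and 49) for subjects with measurable nodal or extranodal disease at screening. The limited examination at treatment visits also covers nodes and spleen (footnote d).

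**6. Size per subject, taking n = 17.**

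- Point estimate: 1/17 = 5.9 percentage points.
- Clopper-Pearson lower 90% limit, change from k − 1 to k responders: smallest at k = 1, 0.3 points; largest at k = 17, 0.8384 − 0.7499 = 0.0885, or 8.9 points from unrounded limits.
- Illustration near the 87.3% CRR that Protocol 1.1.2.2.2 reports for PCYC-1118E: 15/17 = 88.2% (90% CI 67.4 to 97.9) against 14/17 = 82.4% (60.4 to 95.0). The lower limit moves by 0.6738 − 0.6044 = 0.0694, or 6.9 points.

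**The case against.** **Materiality.** The 5.9 points are what any one subject does to any binary endpoint at n = 17, so they are no evidence that the gap will occur. To be lost, a subject must miss the 25% to <50% band at every evaluable visit and never show documented shrinkage, although any shrinkage is enough for PR. CRR is descriptive. All of this stands, and it is why the point is minor.

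**Literalism.** The investigator assigns the category, and the documents specify no programmed derivation. A sensible investigator might treat a deeper IgM fall as at least MR. Attachment 1 itself governs CRR only if the IVth IWWM named in Protocol 11.3.2.1 and SAP 5.3.1 is read as the VIth, as in the stated objectives. Both remarks are fair. They show that the table may not be applied literally, but they do not supply the missing rule.

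**The table is complete.** With SD as the residual, every assessment receives a category, and the criteria are adapted from a cited source. The documents do not show whether the MR cap comes from that source. This argues against amending the MR row without checking. It does not remove the reversal in rank.

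**Stronger readings.** A reader might infer that the primary endpoint is miscounted. The documents do not support that: the literal rule leaves every PR and VGPR cell unchanged. ORR could move only if an investigator recorded PR despite unreduced nodes, which departs from the text. A reader might also infer that every subject with unreduced nodes and a deep IgM fall is lost from CRR. That is not so either, because one evaluable assessment in the MR band, at any time, keeps the subject in.

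**Conclusion.** The point holds as a minor defect in wording. A stated rule ranks a deeper IgM response below a shallower one when baseline nodes or spleen are unreduced and there is no PD. Its reach is the descriptive CRR alone, and it can only lower it. The number of subjects affected cannot be estimated from the documents and may be zero; each would cost 5.9 points.

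This rests on three assumptions: Attachment 1 governs CRR, investigators apply its rows as written, and 17 subjects are treated. A predicted loss in CRR, or any consequence for the study's success criterion, would go beyond the documents.

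**What to change.** Keep the investigator-assessed CRR under Attachment 1 as the reported secondary endpoint. Add one supplementary CRR to SAP 5.3.1 and 5.3.2 that differs from it in this cell only. Suggested text:

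> In addition to subjects counted in the investigator-assessed CRR, a subject is counted as MR if at least one assessment before the start of subsequent anti-cancer therapy shows an IgM reduction from baseline of 50% or more, is not PR or better solely because baseline lymphadenopathy/splenomegaly is not reduced, and is not PD by investigator assessment. IgM is taken by the method prespecified for that subject (protocol 9.2). Baseline is the pre-plasmapheresis value where protocol 8.5/9.2 applies. Values within 35 days after plasmapheresis are not used.

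Three details matter:

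- **Therapy limit.** It applies only to the reclassified assessments. The reported CRR states no such limit, SAP 5.2.3 sets one for ORR only, and Protocol 9.1.4.1 continues follow-up after new therapy. Cutting the whole supplementary CRR at new therapy could push it below the reported one and would mix two changes. As worded, it can only equal or exceed the reported CRR, and the difference isolates the gap.
- **Baseline.** SAP 2.5 takes the last value before first dose, which after plasmapheresis could be lower than the baseline that Protocol 8.5 and 9.2 intend.
- **Method.** Protocol 9.2 allows SPEP or quantitative IgM but requires the same method throughout for each subject.

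The cost is one SAP definition and one extra line in the CRR table, from assessments already scheduled. The downside is a small departure from the literal table, so the line must be labelled supplementary and shown beside the reported CRR. Aligning the MR row of Attachment 1 is optional. It needs a formal amendment (Protocol 17.1) and can wait until the sponsor has checked the cited criteria.

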**Attachment 2: Eastern Cooperative Oncology Group (ECOG) Performance Status Scale**

Grade	Eastern Cooperative Oncology Group Performance Status
0	Fully active, able to carry on all pre-disease performance without restriction
1	Restricted in physically strenuous activity but ambulatory and able to carry out work of a light or sedentary nature, eg, light house work, office work
2	Ambulatory and capable of all self-care, but unable to carry out any work activities. Up and about more than 50% of waking hours
3	Capable of only limited self-care, confined to bed or chair more than 50% of waking hours
4	Completely disabled. Cannot carry on any self-care. Totally confined to bed or chair
5	Dead

Source:

1. Oken MM (1982), Creech RH, Tormey DC, et al. Toxicity and response criteria of the Eastern Cooperative Oncology Group. Am J Clin Oncol 1982;5:649-655.

**Attachment 3: Inhibitors and Inducers of CYP3A**

Examples of inhibitors and inducers of CYP3A can be found at the following website: <https://drug-interactions.medicine.iu.edu/Main-Table.aspx>. The list below reflects information obtained from the website on 20 November 2018.

Inhibitors of CYP3A	Inducers of CYP3A
Strong inhibitors:	
Boceprevir	Barbiturates
Clarithromycin	Carbamazepine
Cobicistat	Efavirenz
Grapefruit a	Glucocorticoids
Indinavir	Modafinil
Itraconazole	Nevirapine
Ketoconazole	Oxcarbazepine
Mibepradil	Phenobarbital
Nefazodone	Phenytoin
Nelfinavir	Pioglitazone
Posaconazole	Rifabutin
Ritonavir	Rifampin
Saquinavir	St. John's Wort
Suboxone	Troglitazone
Telithromycin	
Troleandomycin	
Voriconazole	
Moderate inhibitors:	
Amiodarone	
Amprenavir	
Aprepitant	
Atazanavir	
Ciprofloxacin	
Crizotinib	
Darunavir	
Diltiazem	
Dronedarone	
Erythromycin	
Fluconazole	
Fosamprenavir	
Imatinib	
Seville orange	
Verapamil	
Weak inhibitors:	
Cimetidine	
Fluvoxamine	
All other inhibitors:	
Chloramphenicol	
Delavirdine	
Gestodene	
Mifepristone	
Norfloxacin	
Norfluoxetine	
Starfruit	

a. Also contains moderate CYP3A inhibitors.

**Attachment 4: Child-Pugh Score**

Measure	1 point	2 points	3 points
Total bilirubin, $\mu\text{mol/l}$ (mg/dl)	<34 (<2)	34-50 (2-3)	>50 (>3)
Serum albumin, g/L (g/dl)	>35 (>3.5)	28-35 (2.8-3.5)	<28 (<2.8)
PT INR	<1.7	1.71-2.30	>2.30
Ascites	None	Mild	Moderate to Severe
Hepatic encephalopathy	None	Grade I-II (or suppressed with medication)	Grade III-IV (or refractory)

Points	Class
5-6	A
7-9	B
10-15	C

Source:

1. Child CG, Turcotte JG (1964) "Surgery and portal hypertension". In Child CG. *The liver and portal hypertension*. Philadelphia:Saunders. pp. 50-64.

**Attachment 5: Recommended Dose Modifications of Ibrutinib for Use with CYP3A Inhibitors**

Patient Population	Co-administered Drug	Recommended Ibrutinib Dose for the Duration of the Inhibitor Use a
B-Cell Malignancies	Mild CYP3A inhibitors	420 mg or 560 mg once daily per indication. No dose adjustment required.
	Moderate CYP3A inhibitors	280 mg once daily.
	
 
• Voriconazole
 
• Posaconazole at doses less than or equal to suspension 200 mg BID
 
	140 mg once daily.
	
 
• Other strong CYP3A inhibitors
 
• Posaconazole at higher dosesb
 
	Avoid concomitant use and consider alternative with less CYP3A inhibitory potential If these inhibitors will be used short-term (such as anti-infectives for seven days or less), interrupt ibrutinib.

a. Monitor for adverse reactions to ibrutinib and interrupt or modify dose as recommended.

b. Posaconazole at higher doses (posaconazole suspension 200 mg three times daily or 400 mg twice daily, posaconazole IV injection 300 mg once daily, posaconazole delayed-release tablets 300 mg once daily).

**Attachment 6: Calculated Creatinine Clearance**

Cockcroft-Gault formula:

To calculate the subject's creatinine clearance (CrCl), use the following Cockcroft-Gault formula:

$$\text{CrCl} = (140 - \text{age [in years]}) \times \text{weight (kg)} (\times 0.85 \text{ for females}) / (72 \times \text{serum creatinine [mg/dL]})$$

If the serum creatinine is obtained using the International System of Units (SI) (ie, micromol/L), use the following formula to convert SI units to conventional (mg/dL) units (Manual of Laboratory & Diagnostic Tests, 2004):

- serum creatinine (micromol/L) divided by 88.4 = serum creatinine (mg/dL).

**Attachment 7: New York Heart Association Functional Classification**

NYHA Class Symptoms	NYHA Class Symptoms
I	No symptoms and no limitation in ordinary physical activity, eg, shortness of breath when walking, climbing stairs etc.
II	Mild symptoms (mild shortness of breath and/or angina) and slight limitation during ordinary activity.
III	Marked limitation in activity due to symptoms, even during less-than-ordinary activity, eg, walking short distances (20–100 m). Comfortable only at rest.
IV	Severe limitations. Experiences symptoms even while at rest. Mostly bedbound patients.

## AMENDMENT HISTORY

### SAP Version History Summary

SAP Version	Approval Date	Major Changes
1	25 September 2020	Not Applicable
2	22 April 2022	
Added analysis of primary estimand (section 5.2.3).
 
In section 6.1.1., added Eye Disorders and Other Malignancies in AEs of special interest (AESI).
 
In section 6.1.2., added Cardiac failure, Leukostasis, Hepatic Disorders, Cytopenic Adverse Events, Infections, Tumor Lysis syndrome, Ischemic stroke, Rash. And Other Malignancies has been removed.
 
In section 7, the wording is organized to clarify.

## ABBREVIATIONS

AE	adverse event
BQL	below the quantification limit
CCO	clinical cutoff
CI	confidence interval
CR	complete response
CRF	case report form
CRR	clinical response rate
CSR	Clinical Study Report
CTCAE	Common Terminology Criteria for Adverse Events
DOR	duration of response
ECG	electrocardiogram
ECOG	Eastern Cooperative Oncology Group
eCRF	electronic case report form
IWWM	International Workshop on WM
MedDRA	Medical Dictionary for Regulatory Activities
MR	minor response
ORR	overall response rate
OS	overall survival
PD	progression disease
PFS	progression-free survival
PI	principal investigator
PK	pharmacokinetic(s)
PR	partial response
PT	preferred term
SAE	serious adverse event

---

SAP	Statistical Analysis Plan
SD	standard deviation
SMQs	standardized MedDRA queries
SOC	system organ class
TEAE	treatment-emergent adverse event
TTR	time to response
VGPR	very good partial response
WHO	World Health Organization
WHO-DD	World Health Organization Drug Dictionary
WM	Waldenström's Macroglobulinemia

## 1. INTRODUCTION

This Statistical Analysis Plan (SAP) covers Primary Analysis and Final Analysis specified in the protocol 54179060WAL4001. It contains definitions of analysis sets, derived variables and statistical methods for analyses of efficacy, safety and pharmacokinetic (PK) data of study 54179060WAL4001.

### 1.1. Trial Objectives

#### Primary Objective

The primary objective of this study is to evaluate the efficacy of ibrutinib based on overall response rate (ORR) (partial response [PR] or better) by investigator assessment per the modified Consensus Response Criteria from the VIth International Workshop on Waldenström's Macroglobulinemia (IWWM) (NCCN 2019), in Chinese subjects with relapsed or refractory Waldenström's Macroglobulinemia (WM).

#### Secondary Objectives

Secondary objectives are to evaluate: clinical response rate (minor response [MR] or better) by investigator assessment according to the modified VIth IWWM (NCCN 2019) criteria, Very Good PR (VGPR) or better by investigator assessment according to the modified VIth IWWM (NCCN 2019) criteria; duration of response (DOR) by investigator assessment; time to response (TTR) by investigator assessment; progression-free survival (PFS) by investigator assessment; overall survival (OS); safety and PK of ibrutinib in Chinese subjects with relapsed or refractory WM.

### 1.2. Trial Design

This is a single-arm multicenter, Phase 4 study to evaluate the efficacy and safety of ibrutinib in Chinese subjects with relapsed or refractory WM with symptomatic disease meeting at least 1 of the recommendations from the Second IWWM for requiring treatment.

Approximately 17 subjects will be enrolled into the study. Subjects will receive ibrutinib 420 mg daily until disease progression or unacceptable toxicity, whichever occurs first. Ibrutinib will be supplied as hard gelatin capsules for oral administration.

The study will include a Screening Phase, a Treatment Phase and a Follow-Up Phase. During the Screening Phase, the subjects' eligibility will be determined. The Treatment Phase will extend from first dose of study drug until study drug discontinuation. The Follow-up Phase will consist of the Post-treatment pre-disease progression Phase and a Post-disease Progression Phase. The Post-treatment pre-disease progression Phase will extend from the discontinuation of treatment (for reasons other than disease progression) until the subject has progressive disease, at which point the Post-disease Progression Phase will begin. Subjects who progress on treatment will transition directly to the post disease progression phase. In this latter phase, subsequent anticancer therapy, occurrence of any other malignancy and survival status will be recorded until death, lost to follow-up, consent withdrawal, or study closure. The study is planned to be completed 3 years after the last subject receives first dose.

Clinical cutoffs (CCOs) planned for this study are:

- CCO for the primary analysis is estimated to be performed approximately 12 months after the last subject receives first dose. Alternative appropriate cutoffs will be considered based on regulatory requirement.
- CCO for the final analysis is estimated to occur 3 years after last subject receives first dose.

### **1.3. Statistical Hypotheses for Trial Objectives**

The primary hypothesis for this study is that ibrutinib is an effective agent as measured by ORR (with a point estimate approximately 70% and the lower bound of the 90% confidence interval [CI] is greater than 32%) in Chinese subjects with relapsed/refractory WM.

### **1.4. Sample Size Justification**

Assuming the ORR (PR or better) by investigator is 69.8% in the study population, which is the same as global pivotal study (PCYC-1118E) result, approximately 17 subjects will be required to obtain at least 85% power to declare the ORR is 32% (the minimum clinically meaningful ORR) or higher at the 1-sided significance level of 0.05.

### **1.5. Randomization and Blinding**

This is an open label study, randomization and blinding procedures are not applicable.

## **2. GENERAL ANALYSIS DEFINITIONS**

### **2.1. Visit Windows**

For visit-wise analysis, CRF-recorded visits will be followed.

The visit windows are described in “Time and Events Schedule” of the protocol.

### **2.2. Pooling Algorithm for Analysis Centers**

Data from all study centers will be pooled for analyses.

### **2.3. Analysis Sets**

#### **2.3.1. All Treated Analysis Set**

All Treated analysis set is defined as all enrolled subjects who receive at least 1 dose of study drug.

#### **2.3.2. Safety Analysis Set**

Safety analysis set is defined as all enrolled subjects who receive at least 1 dose of study drug. The safety population is identical to All Treated population.

